Efficacy of Platelet Enriched Plasma in preventing surgery for patients with chronic tympanic membrane perforation

Protocol Version 3; February 7th; January 22, 2018

Background & Rationale

Tympanic membrane (TM) perforation is the leading cause of conductive hearing loss. TM perforations in adults typically arise from middle ear infections, trauma, or from iatrogenic cause. While approximately 80% TM perforations close with time and conservative managements, approximately 20% require surgical intervention[1-3]. Often before exploring surgical options some patients opt for trial for paper patch myringoplasty that can be performed in the clinic. Success rates with paper patch myringoplasty are variable and can range from 12 to 63% depending on whether the size of the perforation is large or small[4]. When patients fail conservative treatment with paper patch, patients will explore surgical options. Surgical success rates for myringoplasty vary and quoted ranging from 60 - 90% in adults to 34-85% in children, and often lower in anterior TM perforations secondary to more difficult exposure[1]. Of those patients that do require surgical intervention, costs of tympanoplasty can cost upwards of twenty-four thousand dollars[5].

Multiple different biologic materials have been heavily investigated in the literature including hyaluronic acid, heparin, epidermal growth factor, fibroblast growth factor, platelet derived growth factor, and transforming growth factor with variable success[6]. Recently platelet enriched plasma (PRP) has been favored in multiple surgical procedures from orthopedics, ENT, to plastic surgery[7, 8]. The rationale behind its use are two fold; first platelets play a fundamental role in hemostasis and wound healing, and secondly the alpha granules contained within platelets contain various growth factors that play a fundamental role in wound healing[9]. Currently there are three different PRP that are FDA approved, SMARTPEP (SmartPEP, Harvest Technologies Corp, Norwell, MA) and Platelet Concentrating Collection Systems (3i/Implant innovations, Palm Beach Gardens, FL), and Arthrex (Arthrex Naples, FL) [2]. PRP is an autologous blood donation, where whole blood is collected from the patient and subsequently isolated through differential gradient centrifugation in an anticoagulant citrate dextrose-A[2].

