We wish to pursue and investigate the use of PRP in a clinical setting as the sole treatment for small tympanic membrane perforations. While no studies exist on the specific use of PRP as sole treatment modality, multiple studies have shown success with various growth factors such as PDGF and ECF[17]. PRP is promising because its ability to use a variety autologous growth factors stored within their alpha granules, negating the need for exogenous growth factors. Ultimately if PRP can increase the rate of tympanic membrane perforation healing thus negating the need for surgical intervention, PRP can potentially save the health care industry millions of dollars every year.

Specific Aim

The goal of our proposed prospective project is to investigate the efficacy of platelet enriched plasma (PRP) as a treatment for patients with chronic tympanic membrane perforation. Our primary outcome includes the prevention of patients requiring surgery for their perforation.

Inclusion Criteria

- Patients aged 18 or older
- Patients who have a chronic anterior tympanic membrane perforation that is <50% of the eardrum who meet criteria for tympanoplasty procedure
- Patients willing to comply with the protocol and attend all study visits.
- Patients is able to provide written informed consent

Exclusion Criteria

- Patients who are aged 17 or younger
- Patients who have previously undergone middle ear or lateral skull base surgery
- Patients who have a chronically draining ear who would not qualify for a tympanoplasty
- Any type of platelet disorder, cancer, or ongoing systemic infection.
- Any type of hemodynamic instability, septicemia, infection, tobacco use, any use of steroids to the ear drums, and patient unwilling to accept the risks of the procedure.
- Type I diabetes or other autoimmune pathology (based on case report by Kaux et al (2014) [11])

Benefits and Risks

There are some risks associated with a tympanoplasty, however, these risks are not associated with this study and will be covered in a separate consent for surgery.

There is a minimal risk for patients associated with the possibility for an unintentional breach of confidentiality. All records will be adequately protected to assure that this risk is minimized to the best of our ability.

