Step 4: Run the centrifuge at 1500 rpm for 5 minutes. Remove the syringe, taking care to keep it in an upright position to avoid mixing the plasma and red blood cells.

Step 5: Transfer 4-7ml of the ACP from the larger outer syringe into the small inner syringe that comes with the kit. Slowly push down the outer syringe's red wings, while slowly pulling up the plunger of the small inner syringe. Final concentration of platelets is estimated around $600 \times 10^3 / \text{ul}$.

Step 6: Unscrew the small inner syringe. The ACP is ready for use at the point of care. The ACP can also be transferred into a sterile cup on the sterile field and transferred into a 10ml syringe for use. The ACP should be used within 4 hours after blood draw. For this procedure, we will use immediately after isolating.

Step 7: Once the ACP is isolated and ready to use it will be applied directly to the small tympanic membrane perforation with the use of the otomicroscope.

Patient follow up. We will ask patients to remain in the clinic for 30 minutes after the injection to assure the safety in the acute post-treatment period including bleeding, vertigo, ear fullness, pain, erythema, swelling, or other signs of inflammation or infection. We will conduct a phone interview between 3-5 days after application of PRP. During this phone interview conducted by study team members, we will again evaluate any concerning side effects with questions about the same issues mentioned above and any worsening of hearing loss or discomfort. Each subsequent follow-up visit will evaluate the safety of the treatment with the same endpoints and additionally include an assessment of efficacy.

The objective study outcomes will be in terms of success of healing of tympanic membrane, and pictures taken in clinic will be the data collected. The pictures taken of the perforation will be standardized to the size of the malleus in order to compare images between different visits.

Patients who do not have complete closure of the tympanic membrane will proceed to surgery as originally planned and resume routine follow-up. Should any patients achieve full closure and healing they will have their surgery cancelled and resume routine follow-up.

A full schedule of events for each study visit is included below.

Schedule of Events

	Treatment Visit	Post injection Follow up phone Call	Follow up Visit 1	Follow up Visit 2	Final Follow
	Day 0	Day 3-5	Day 14	Day 28	Day 42
Visits	1	N/A	2	3	4

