Medical History and Current Medications	X				
Ringing in the Ear Evaluation	X	X	X	X	x
Overall Exam	X		X	X	x
Blood Samples	X				
Questionnaires	X	X	x	X	X
Hearing Test	X				X
Ear Exam	X		X	X	X
Eardrum Mobility Test	X				X
Balance Testing	X		X	X	X
Study Treatment Application	X				
Review Current Medications and Side Effects	X		X	X	X
Signs of Infection, edema, or Inflammation	X	X	X	X	X
Photographs of Eardrum	X		X	X	X
Approximate Study Visit Length (in hours)	2 hours	5-10 minutes	0.25 hour	0.25 hour	0.25 hour

While the principal investigator, [name], has had limited exposure to the use of PRP we as ENT residents have used it on a consistent basis during our facial plastics procedures. More specifically we apply it after rhytidectomy (face lift) to help with healing and decrease post-operative hematomas. We perform about 15-20 rhytidectomies a year. Furthermore, we will not have a control arm because those subsets of patients already exists in a day to day basis in the Neurotology clinic. The control arm would be standard patients that do not wish to participate in the study and simply wish to schedule surgery for tympanoplasty. Our aim with this initial study is to understand and evaluate the potential efficacy of platelet enriched plasma (PRP) as a treatment for patients with chronic tympanic membrane perforation. If preliminary data does suggest PRP may be beneficial, our next step is to perform a larger randomized prospective study.

Data Management and Security

To ensure the privacy and confidentiality of data collected from patients, data will be stored in REDCap, a password protected database accessible only by the relevant study personnel. No identifying information such as medical record number, date of birth or social security number will be collected.

Monitoring and Reporting Unanticipated Problems

The attached questionnaire will be utilized to identify any problems with the study that may be causing patient discomfort or problems. The results of these questionnaires will be discussed at regular meetings with the study personnel to determine to continue or discontinue the study. Any adverse events noted during the follow-up will also be reviewed. Any problems identified will be promptly reported according to the requirements of the KU Human Subjects Committee standard operating procedures.

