This study will only be stopped prior to consenting all patients if there is a serious adverse event deemed to be connected with the application of the PRP. Patient's will be followed closely, including a follow up phone call 3-5 days post application, at the pre-arranged clinic visits, or at any point if a patient has significant concerns or symptoms. Multiple large systematic reviews and Cochrane data base reviews have found no associated complications with PRP compared to controls. However there are case reports with possible adverse events, including inflammatory reaction, in patients with autoimmune issues such as diabetes type I. In both the phone interview and clinic follow up we will ask and examine for any signs of excessive inflammation or reaction; specifically looking for erythema, drainage, swelling, edema, pruritus, or other inflammatory symptoms. After five subjects have been enrolled, we will look at cumulative adverse events and the number of subjects needed to proceed. We have appointed [name], a Neurologist, who will serve as an independent safety monitor to review any adverse events. If after five subjects or any other point the study is deemed unsafe or delaying standard of care, we will terminate the study.

Statistical Analysis Plan and Sample Size

Chi-square and Fischer exact tests will be used to test for whether or not patients were able to avoid surgery. Time to healing analysis will also be completed. Statistical significance will be based on an *a priori* designation of $p \leq 0.05$. Demographic variables and clinical variables will be summarized using descriptive statistics.

A minimum of 10 patients will be enrolled in this pilot study. Patients will not be randomized as a part of this study. Due to the pilot nature of this study and the absence of any prior data to build sample size calculations, this exploratory group should provide data for future studies and justify future sample size calculations.

Bibliography

1. Aggarwal, R., S.R. Saeed, and K.J. Green, *Myringoplasty*. J Laryngol Otol, 2006. **120**(6): p. 429-32.
2. Arora, N.S., et al., *Platelet-rich plasma: a literature review*. Implant Dent, 2009. **18**(4): p. 303-10.
3. Kristensen, S., *Spontaneous healing of traumatic tympanic membrane perforations in man: a century of experience*. J Laryngol Otol, 1992. **106**(12): p. 1037-50.

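### The only comparator the protocol names cannot show how many comparable ears close without PRP, so any natural closure in treated ears would be credited to PRP

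*Combined protocol and SAP*

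**What the plan says.** The Specific Aim sets the endpoint: "Our primary outcome includes the prevention of patients requiring surgery for their perforation". For treated patients, the follow-up text in Protocol for Preparation states how avoidance comes about: "Should any patients achieve full closure and healing they will have their surgery cancelled and resume routine follow-up". The Schedule of Events gives them ear examinations and photographs at Days 14, 28 and 42.

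On controls, the text after the Schedule of Events table says "we will not have a control arm because those subsets of patients already exists in a day to day basis in the Neurotology clinic", and then "The control arm would be standard patients that do not wish to participate in the study and simply wish to schedule surgery for tympanoplasty". No number, period, matching, examination or data collection is given for that group.

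Study Procedures says that taking part can alter surgical plans only if PRP heals the perforation. It also says that preventing surgery in one of 10 patients would be financially justifiable, and that the review at 10 patients leads to stopping if none has measurable benefit.

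Statistical Analysis Plan and Sample Size says "Chi-square and Fischer exact tests will be used to test for whether or not patients were able to avoid surgery", with significance at p ≤ 0.05. It names no comparator. It sets a minimum of 10 patients and says of them that "this exploratory group should provide data for future studies and justify future sample size calculations".

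**The concern.** A claim that PRP prevents surgery needs to know how many similar ears would have closed anyway. The named group cannot supply this. Its members are recognised by wanting an operation, nobody is asked to check or record whether their perforation closes, and they are not restricted to patients who satisfy the exclusions (tobacco use, type I diabetes, platelet disorder, cancer, steroids to the eardrum).

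If that group is counted as having no avoided operations, or is simply not observed, the whole treated closure rate is read as the effect of PRP. The error can only favour PRP. It also touches the planned randomized study, whose sample size depends on an untreated closure rate as well as a PRP rate.

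**Working it through.** **Figure in the plan.** The minimum of 10 has no rate, effect size or power behind it, as the plan says, so there is nothing to reproduce.

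**Inputs.** From the documents: n = 10 treated and significance at p ≤ 0.05 (sidedness not stated; two-sided used here). Assumed, because the documents do not give them: the natural 6-week closure rate p0 in eligible ears (2%, 5%, 10%, with 20% as an upper case) and the number of controls m (10, 20, 50, 200).

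**Step 1: bias of the estimate.** With control avoidance taken as 0, the risk difference is the treated closure proportion minus 0. If PRP is inert, its expected value is p0 rather than 0.

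**Step 2: at least one closure under an inert treatment.** P = 1 − (1 − p0)^10.
- p0 = 2%: 1 − 0.98^10 = 0.183
- p0 = 5%: 1 − 0.95^10 = 0.401
- p0 = 10%: 1 − 0.90^10 = 0.651

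**Step 3: Fisher's exact test against 0 of m controls.** First find the smallest number r of closures in 10 that gives two-sided p ≤ 0.05. The chance that an inert treatment reaches it is then P(X ≥ r), with X binomial(10, p0).

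| m | smallest r (p) | p0 = 5% | p0 = 10% | p0 = 20% |
|---|---|---|---|---|
| 10 | 5 (0.033) | 0.01% | 0.2% | 3.3% |
| 20 | 3 (0.030) | 1.2% | 7.0% | 32.2% |
| 50 | 2 (0.025) | 8.6% | 26.4% | 62.4% |
| 200 | 1 (0.048) | 40.1% | 65.1% | 89.3% |

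For example, with m = 50 and p0 = 10%: 1 − 0.9^10 − 10 × 0.1 × 0.9^9 = 1 − 0.3487 − 0.3874 = 0.264. The uncorrected chi-square test is more lenient: 4/10 suffices against 0/10 (p = 0.025) and 1/10 against 0/50 (p = 0.024).

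For contrast, if controls were examined in the same way and shared p0, the chance of a significant Fisher result favouring PRP would be at most 2.6% over p0 from 2% to 30% and m from 10 to 200.

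**Step 4: the later randomized study.** This is an illustration with an assumed 40% closure on PRP, 80% power and two-sided 5%. With p̄ = (p1 + p2)/2, the number per arm is

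n = [1.96√(2p̄(1 − p̄)) + 0.842√(p1(1 − p1) + p2(1 − p2))]² / (p1 − p2)².

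For p2 = 2%, 5%, 10% and 20% this gives 16.8, 21.1, 31.5 and 81.2 per arm before rounding up, a ratio of 81.2/16.8 = 4.8. The normal approximation is rough at the low rates: with Fisher's test, 17 and 21 per arm give about 76% and 75% power for p2 = 2% and 5%. The spread is what matters here.

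**The case against.** **The study is a declared pilot.** It is described as initial, exploratory and non-randomized, with a randomized study to follow. Having no concurrent control is a disclosed choice and not in itself a fault. That stands. What remains is that the protocol offers clinic patients as a substitute for the missing control, and that role they cannot fill.

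**A reader might infer that the controls' avoidance is fixed at zero by construction, because they are selected on the outcome.** The text does not go that far. They wish to schedule surgery, and treated patients too are already scheduled when they enrol. A decliner's operation could be cancelled in routine care if the ear closed. The difference is that no such closure would be looked for or recorded. Nor do all decliners differ on eligibility: only eligible patients are approached, so some will meet the criteria, although the control sentence is not limited to them.

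**A reader might infer that a significance test against decliners is planned.** The SAP never says so, and the control sentence is conditional. But two-group tests are listed and no other group is named. In a purely single-arm reading, the attribution of every closure to PRP remains. The Study Procedures sentence on surgical plans is meant partly as reassurance about access to surgery, yet it too leaves no room for closure without PRP.

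**A reader might take the background rate from Background & Rationale:** "While approximately 80% TM perforations close with time and conservative managements, approximately 20% require surgical intervention". That figure covers all perforations, with no time limit. Eligible ears are chronic and meet criteria for tympanoplasty, so it should not be used for them. No minimum duration defines chronic, however, so a rate of nil cannot be assumed either.

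**One closure in 10 is not statistical significance.** That is correct. With only 10 controls at zero, Fisher's test is hard to pass by chance. The risk becomes serious only with more controls, and their number is not stated.

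**Conclusion.** The concern holds in this form: the only named comparator cannot measure closure without PRP, and the analysis has no other, so natural closure in treated ears would be counted as surgery prevented by PRP. The direction of the bias is certain; its size is not.

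At an assumed 10% natural closure, an inert treatment reaches the one-in-10 level 65% of the time. A false-positive Fisher result against a zero control has a chance of 0.2% with 10 controls and 26% with 50. These figures rest on assumed values of p0 and m, neither of which is in the documents.

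It would be too strong to say that the pilot fails its purpose of informing sample size. It can supply a PRP closure estimate; it cannot supply the untreated rate that the same calculation needs, and that rate would have to come from elsewhere.

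**What to change.** 1. After the Schedule of Events table, delete the statement that patients who schedule surgery are the control arm. Say that the study is single-arm.
2. In Statistical Analysis Plan and Sample Size, replace the chi-square/Fisher test of surgery avoidance with the proportion of treated ears with complete closure by Day 42 and its exact 95% confidence interval. With 10 ears, for example, 0/10 gives 0% to 30.8%, 1/10 gives 0.3% to 44.5%, and 4/10 gives 12.2% to 73.8%.
3. Limit the conclusion to closure after PRP. Make no statement that PRP prevented surgery.
4. Optionally, with ethics committee approval, abstract from routine pre-operative or operative notes whether the perforation was open or closed, with days since consultation, for untreated patients who meet the same criteria. Report this as a descriptive background rate and use it in planning the randomized study. State that it is not a second group for significance testing.

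Items 1 to 3 cost only wording. Item 4 needs an ethics request and a short chart review, with no added visits. The downside is a more modest claim. Any chart rate stays non-randomized and may be incomplete, since routine notes may not record perforation size, site, duration or the exclusions consistently.

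### The surgery-avoidance test (chi-square and Fisher exact, p≤0.05) has no comparator, grouping factor or null proportion in a single-group pilot, so it gives no informative p-value as written

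*Combined protocol and SAP*

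**What the plan says.** The Specific Aim section states: "Our primary outcome includes the prevention of patients requiring surgery for their perforation". The only test given for that outcome is in the Statistical Analysis Plan and Sample Size section, which reads: "Chi-square and Fischer exact tests will be used to test for whether or not patients were able to avoid surgery". The significance level there is p≤0.05, with no sidedness. The same section adds "Time to healing analysis will also be completed", "Patients will not be randomized as a part of this study" and "A minimum of 10 patients will be enrolled in this pilot study".

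The text after the Schedule of Events table says "we will not have a control arm because those subsets of patients already exists in a day to day basis in the Neurotology clinic". It then describes a notional comparator: "The control arm would be standard patients that do not wish to participate in the study and simply wish to schedule surgery for tympanoplasty". No number, period, data collection or analysis is given for those patients, and the statistical section does not mention them.

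Background & Rationale quotes paper-patch success of 12 to 63%, varying with perforation size. The plan does not adopt either figure as a reference rate. It specifies no estimate or interval for the primary outcome.

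**The concern.** A chi-square or Fisher exact test on a contingency table asks whether an outcome differs between groups, and here there is one group. A one-sample chi-square asks whether a proportion differs from a stated value, and no value is stated. The sentence therefore names a test without a hypothesis.

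The contrast would have to be chosen when the analysis is run, possibly with the outcomes known. With about ten patients, that choice can put the same result on either side of 0.05. A significance statement in the pilot report would then reflect the chosen contrast more than the treatment. It would also feed into the case for the follow-on trial, since the protocol says: "If preliminary data does suggest PRP may be beneficial, our next step is to perform a larger randomized prospective study".

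**Working it through.** **Inputs.** n=10 is the stated minimum; no maximum is given. Alpha is 0.05. The rates 12% and 63% are the ends of the paper-patch range in Background & Rationale. The number of decliners (m = 10, 20, 50) and their having no surgery avoided are assumptions, because the documents give neither. The plan has no figure of its own to reproduce: the 10 patients are not derived from a power calculation, and the section says so.

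**1. Treated group alone as a contingency table.** One row and two columns give (1−1)×(2−1) = 0 degrees of freedom. Expected counts equal observed counts, so for 3 avoided and 7 not, the statistic is 0 and software returns p=1. Fisher's test with an empty second row also returns p=1. Neither value depends on the outcome.

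**2. One-sample chi-square with a default 50/50 null (1 df).**
- 0/10: (0−5)²/5 + (10−5)²/5 = 10, p=0.0016.
- 10/10: the same statistic, p=0.0016.

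Complete failure and complete success are equally significant.

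**3. Fisher exact against decliners.** With x of 10 treated and 0 of m decliners avoiding surgery, the probability of the observed table is C(10,x)/C(10+m,x). For x=3:

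| Assumed m | Calculation | Two-sided p | Smallest significant result |
|---|---|---|---|
| 10 | 2×120/1140 | 0.21 | 5/10 (p=0.033; 4/10 gives 0.087) |
| 20 | 120/4060 | 0.030 | 3/10 (2/10 gives 0.103) |
| 50 | 120/34220 | 0.0035 | 2/10 (p=0.025; 1/10 gives 0.167) |

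At m=10 the opposite tail is equally probable and is doubled in. At m=20 and m=50 it is more probable than the observed table and is not counted. The treated result is the same in each row; only the number of decliners changes.

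**4. One-sided exact binomial against a background rate**, P(X≥x | n=10, p0), for illustration:
- p0=0.12: 3/10 gives 0.109 and 4/10 gives 0.024, so 4/10 is needed.
- p0=0.63: 9/10 gives 0.068 and 10/10 gives 0.63¹⁰ = 0.0098, so 10/10 is needed.

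**5. What ten patients do support: exact (Clopper-Pearson) 95% intervals.**

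| Avoided surgery | 95% CI |
|---|---|
| 0/10 | 0 to 31% (upper limit 1−0.025^(1/10) = 0.308) |
| 1/10 | 0.3 to 45% |
| 3/10 | 7 to 65% |
| 5/10 | 19 to 81% |

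**The case against.** The strongest reply is that the investigators had a comparison in mind: treated patients against clinic patients who decline the study. On that reading the test can be computed, and the fault is poor specification and confounding. This is a plausible account of intent, but it does not repair the plan. The same paragraph says there is no control arm, and the statistical section never takes the decliners up. They are also defined by wanting surgery, and they have no study visits at which closure could lead to cancellation. Their avoidance rate is therefore near zero by selection, and the p-value would depend on how many of them are counted.

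A second reply is that enrolled patients are already scheduled for surgery, so the implied null is zero avoidance. The plan does not say this. With p0=0, P(X≥1) = 1−(1−0)¹⁰ = 0, so a single success would reject and the test would add nothing to the count.

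A third reply is that an exploratory pilot with no decision tied to p should not be held to this standard. That limits the consequence, but it also favours estimation: the stated purpose is to inform later sample-size calculations, which need a proportion and its uncertainty.

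The time-to-healing analysis does not fill the gap. It addresses a different quantity and supplies no contrast for this test.

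**Conclusion.** The point holds and should be fixed. The only test named for the primary outcome has no hypothesis attached, and it yields either a constant p-value or one set by an unstated choice. The figures assume n=10; those in step 3 also assume the number of decliners and that all of them have surgery.

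A reader might infer more than the documents support:
- *That the test has 0 degrees of freedom under any reading.* This is true only of the one-row contingency table. A one-sample chi-square has 1 df but needs a null that is not given.
- *That 12% and 63% are equally eligible nulls for this trial.* The protocol ties the range to perforation size, enrols perforations under half of the eardrum and elsewhere calls them small. The two ends only illustrate how much the choice matters.
- *That the roughly 80% closure quoted in the background is a candidate null.* It describes perforations generally, not chronic ones already meeting criteria for tympanoplasty.
- *That a decision rides on the p-value.* The reviews after 5 and 10 patients in Study Procedures turn on benefit and adverse events. The harm is confined to reporting and to planning the randomized study.
- *That 10 patients is the wrong number.* Nothing here shows that.

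**What to change.** Delete the chi-square/Fisher sentence, and the p≤0.05 criterion as it applies to this outcome. Replace them with wording such as:

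*The primary analysis is the proportion of all treated patients who avoid surgery with documented complete closure by the last study visit, with an exact Clopper-Pearson 95% confidence interval. Patients without documented closure count as not avoiding surgery. No inferential comparison will be made with patients who decline the study.*

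If a p-value is kept, state one null proportion with its justification and its sidedness before any outcome is seen, and use a one-sample exact binomial test.

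The cost is SAP wording. No patients, visits or data are added, because the ear is already examined and photographed at each clinic visit through Day 42. There are two downsides: a wide descriptive interval replaces a significance claim, and counting undocumented closure as failure may understate success. A single group still cannot separate the effect of PRP from spontaneous closure; that is left to the randomized study.

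A separate matter bears on the endpoint but does not cause this defect. Study Procedures puts surgery at 5-8 weeks in two places (5×7=35 to 8×7=56 days) and says in another that cases are booked about 3 months out. These statements must be reconciled with each other and with the Day 42 visit.
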